### PATIENT ELIGIBILITY AND WITHDRAWAL CRITERIA

## **Eligibility and Number of Patients**

This amendment applies to patients who remain on either CO-1686 or erlotinib on the CO-1686-022 study. No additional patients will be enrolled.

### Withdrawal Criteria

The patient has the right to stop treatment or to withdraw from the study at any time.

Patients will continue to receive treatment until one of the following cessation criteria applies:

- Consent withdrawal at the patient's own request or at the request of their legally authorized representative.
- Progression of patient's underlying disease.
  - o Post-progression treatment is permitted, at the discretion of the Investigator and with the approval of the sponsor.
- Intercurrent illness that prevents administration of treatment
- Any event, adverse or otherwise, that, in the opinion of the investigator, would pose an unacceptable safety risk to the patient.
- Major noncompliance that may affect patient safety.
- Pregnancy.
- Investigator decision.

In addition, the sponsor may discontinue the trial early for any of the reasons noted in Section 13.6 of the protocol.

The date and reason for cessation of treatment will be documented. Patients with ongoing SAEs will be followed until either resolution or stabilization has been determined.

#### STUDY PROCEDURES

### **Schedule of Assessments**

The procedures and assessments to be performed are outlined in the Schedule of Assessments presented in Appendix D Tables 4. Procedures are synchronized with administration day of treatment unless indicated. The revised evaluations should commence immediately after the patient is consented, maintaining previous treatment cycle and day sequence.

### Table 4. Schedule of Assessments for All Patients

Procedure	Prior to beginning Amendment 3 Evaluations	Day 1 of each cycle	End-of-Treatment Visit (28 ± 7 days after last dose)
Informed Consent	X		
Physical Examination including vision check		X	X
Vital Signs a and Weight		X	X
Concomitant Medications and Procedures		X	X
Contraceptive Counseling b			X
Serum Pregnancy Test c			X
Local hematology including reticulocytes d		X	X
Local fasting Serum Chemistry e		X	X
Adverse events, including SAEs/AESIs f		X	X
CO-1686 dispensing/ administration		X	
Patient diary g		X	X
ECG Assessments using central ECG machine h		X	X
Tumor Scans i	To be done per institution standard of care or 8 ± 1 weeks during treatment; scans are not required at the End of Treatment Visit		
Blood for CYP Evaluation (Optional Sampling)		X j	

a = Vital signs (blood pressure, pulse, and temperature) taken predose on drug administration days.

<sup>b= Patients are to continue using effective contraception for 12 weeks after last dose of CO-1686 or 2 weeks after the last dose of erlotinib and report any pregnancies during this period.

<sup>c = Serum β-hCG to be evaluated by local lab will be performed only on women of childbearing potential.

<sup>d= Includes hemoglobin, hematocrit, WBC and differential (with ANC), platelet count, and reticulocyte count - on Day 1 at each cycle, and at end-of-treatment. Blood will be analyzed by a local laboratory to inform patient treatment decisions, and must be reviewed by the investigator prior to start of CO-1686 or erlotinib administration. Additional tests may be performed at the investigator's discretion.

<sup>e = Includes total protein, albumin, creatinine, BUN or urea, total bilirubin, alkaline phosphatase, ALT, AST, fasting glucose, sodium, potassium, chloride, magnesium, CO2, calcium, phosphorus, total cholesterol, HbA1c - on Day 1 at each cycle, and at end-of-treatment. Samples will be analyzed by a local laboratory. Fast is defined as 8 hour fast (no food or liquid other than water). HbA1c will be measured every other visit (Cycles 3, 5, 7, etc.) after initiating study drug.

<sup>f= Patients will be monitored for AEs/SAEs/AESIs from the time the first dose of CO-1686 or erlotinib is administered through 28 days after the last dose.

g= Patient diaries should be collected and reviewed for compliance at each visit. No diary will be dispensed at end of treatment.

h=12-lead ECG (in triplicate, 10-sec tracings > 2 min apart) prior to dosing up to and including Cycle 12, at a minimum. For patients who are ongoing at this time and for whom QT has been < 470 ms throughout the study, ECG monitoring may be subsequently taken every 3rd cycle thereafter. ECGs will be performed and interpreted locally for patient care decisions; however, tracings should be submitted to the central lab for independent evaluation.

<sup>i=Tumor scans will no longer be required to be submitted to a central reviewer; Disease progression to continue to be assessed locally by the Investigator. If a patient discontinues treatment before progression or is continuing treatment post progression (approval from Sponsor is required), then the decision to conduct additional scans and the frequency of those scans to monitor disease progression will be the responsibility of the treating physician.

<sup>j= Only one sample is needed and may be collected at any visit to enable NAT2 analysis.

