### 6.3 Exclusion Criteria

Any of the following criteria will exclude patients from study participation:

- 1. Documented evidence of an exon 20 insertion activating mutation other than A763\_Y764insFQEA in the EGFR gene
- 2. Prior treatment with cytotoxic chemotherapy for advanced NSCLC; neoadjuvant/adjuvant chemotherapy is permitted if at least 6 months has elapsed between the end of chemotherapy and randomization
- 3. Active second malignancy; i.e., patient known to have potentially fatal cancer present for which he/she may be (but not necessarily) currently receiving treatment
  - Patients with a history of malignancy that has been completely treated, and currently with no evidence of that cancer, are permitted to enroll in the trial provided all chemotherapy was completed > 6 months prior and/or bone marrow transplant > 2 years prior to first day of study treatment, C1D1
- 4. Known pre-existing interstitial lung disease (ILD)
- 5. Brain metastases
- 6. Treatment with prohibited medications (e.g., concurrent anticancer therapy including other chemotherapy, radiation, hormonal treatment [except corticosteroids and megesterol acetate], or immunotherapy) ≤ 14 days prior to first day of study treatment, C1D1
- 7. Patients who are currently receiving treatment with any medications that have the potential to prolong the QT interval if that treatment cannot be either discontinued or switched to a different medication (not known to affect QT interval) prior to C1D1

- See http://crediblemeds.org/ for a current list of QT-prolonging medications
- 8. Prior treatment with EGFR-TKIs (e.g., erlotinib, gefitinib, neratinib, afatinib, AZD9291, or dacomitinib), CO-1686, or other drugs that target mutant EGFR
- 9. Any of the following cardiac abnormalities or history
  - Clinically significant abnormal 12-lead ECG, QTCF > 450 ms
  - Inability to measure QT interval on ECG
  - Personal or family history of long QT syndrome
  - Implantable pacemaker or implantable cardioverter defibrillator
  - Resting bradycardia < 55 beats/min

- 10. Non-study related surgical procedures  $\leq$  7 days prior to C1D1. In all cases, the patient must be sufficiently recovered and stable before treatment administration.
- 11. Females who are pregnant or breastfeeding
- 12. Refusal to use adequate contraception for fertile patients (females and males) during study treatment and for 12 weeks after the last dose of CO-1686 and 2 weeks after the last dose of erlotinib

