## Management of Prolonged QTc

ECGs will be measured throughout the study as described in the protocol. Readings for QTc prolongation will be based on the average seen in the ECGs for each time point. Patients are required to have laboratory values for potassium and magnesium within normal limits at enrollment, and these electrolytes should be maintained within range during CO-1686 treatment, if necessary using supplementation. If QTC prolongation of CTCAE Grade 3 is observed, CO-1686 will be held until the event has improved to Grade 1. CO-1686 can then be re-started at a reduced dose upon approval by sponsor. After 2 dose reductions, if CTCAE Grade 3 or above QTc prolongation recurs, then CO-1686 will be discontinued unless agreed with the sponsor that additional dose reduction may be considered. If QTC prolongation changes of CTCAE Grade 4 are observed at any time, CO-1686 will be discontinued permanently.

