#### 11.2.5.5 12-lead Electrocardiograms

ECG intervals will be stratified into categories indicative of potential clinical significance. Each patient's maximum QTcF intervals from the pretreatment visit and treatment period visits will be classified as  $\leq 450$  ms, > 450 to  $\leq 480$  ms, > 480 to  $\leq 500$  ms, and > 500 ms. For each patient's maximum change from the pretreatment ECG visit for QTc, intervals will be classified into < 30 ms,  $\geq 30$  to < 60 ms, and  $\geq 60$  ms. The number and percentage of patients in each classified category will be presented. Additional endpoints will include abnormal T waves and U waves and other ECG intervals and diagnostic parameters.

Descriptive statistics will be used to summarize other ECG parameters of PR, QRS, QT, and RR interval, and the corresponding changes from pretreatment ECG visit at each time point. Plots of the mean QT/QTc over time for C1D1 and End-of-Treatment/pretreatment ECG day measurements will be provided.

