Appendix D, Table 3. QTcF Changes on ECG by Acetylator Status

	Overall (N = 635)		
	Slow (n = 300)	Intermediate (n = 259)	Rapid (n = 76)
QTcF Post-baseline ≥ 450 msec	198 (66%)	131 (51%)	34 (45%)
QTcF Post-baseline ≥ 481 msec	92 (31%)	44 (17%)	7 (9%)
QTcF Post-baseline ≥ 501 msec	59 (20%)	22 (9%)	1 (1%)
Two of more within 3 days ≥ 501 msec	19 (6%)	10 (4%)	0 (0.0)
QTcF Change from Baseline > 30 msec	246 (82%)	171 (66%)	47 (62%)
QTcF Change from Baseline > 60 msec	141 (47%)	57 (22%)	9 (12%)

**Abbreviation:** ECG=electrocardiogram.

For those patients ongoing on CO-1686 trials, informed consent and testing for NAT2 polymorphism status will be offered and the results will be shared with the treating physician. It will be up to the patient in consultation with the treating physician to decide continued participation in the trial in light of the acetylator status results or whether alternative treatment options should be sought.

Regardless of acetylator status, monitoring should be the same for all patients receiving CO-1686 whilst on treatment.

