Both the hyperglycemia and QTc management guidelines (Section 7.4) should be followed during this extension phase and any modifications/deviations from these guidances should be discussed and agreed upon with the sponsor prior to implementation.

Once study treatment has been discontinued and the End of Treatment visit has been completed, study participation will cease. Investigational centers will interpret tumor scans locally for the purpose of making treatment decisions and for final tumor response evaluation. The study will close once all patients have either completed participation, have transferred to a locally approved treatment access program (e.g. a named patient program) in accordance with relevant local regulations or the sponsor decides to close the study.

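### The extension-phase rule for spacing out ECGs is written on uncorrected QT, so read literally it admits some patients with QTcF of 470 ms or more

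*Combined protocol and SAP*

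**What the plan says.** The rule appears twice in Appendix D. Footnote h of Table 4 requires triplicate ECGs before dosing every cycle through at least Cycle 12, then relaxes the schedule for ongoing patients "for whom QT has been < 470 ms throughout the study, ECG monitoring may be subsequently taken every 3rd cycle thereafter". The procedures for Day 1 of each cycle repeat the same QT condition, "for whom QT has been < 470 ms throughout the study". Neither place names a correction formula.

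Elsewhere the plan works with corrected intervals:
- Section 6.3, exclusion criterion 9, excludes QTcF above 450 ms.
- Section 3.2.1 reports earlier safety experience as QTcF above 500 ms.
- Section 11.2.5.5 bands the maximum at 450, 480 and 500 ms: "Each patient's maximum QTcF intervals from the pretreatment visit and treatment period visits will be classified".
- The extension phase's own ECG table is titled "Appendix D, Table 3. QTcF Changes on ECG by Acetylator Status".
- Section 7.4.1 bases dose action on QTc, without naming the formula: "Readings for QTc prolongation will be based on the average seen in the ECGs for each time point".

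Section 11.2.5.5 also lists uncorrected QT in its own right: "Descriptive statistics will be used to summarize other ECG parameters of PR, QRS, QT, and RR interval".

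**The concern.** QT shortens as heart rate rises, so a fixed limit on raw QT means different things at different rates. At faster rates, a patient with a long corrected interval can satisfy it. This is the only rule in the plan that reduces ECG monitoring, and Section 3.2.1 states that CO-1686 lengthens QTc. The requirement that the limit hold for the whole study suggests the rule is meant to pick out patients whose ECGs have been consistently reassuring. On the literal wording it can also pick out patients whose QTcF was not.

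What is at stake is later detection of a further rise in patients already at QTcF of about 470 to 500 ms. No effect on the ECG safety summaries or on any efficacy result is claimed.

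**Working it through.** There is no figure in the plan to reproduce. The check converts the stated limit to QTcF.

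**Inputs**
- QT limit: below 470 ms (Appendix D, Table 4, footnote h, and Day 1 procedures), so 469 ms is the largest whole value that passes.
- Correction: Fridericia, which the plan names. The standard formula, not printed in the plan, is QTcF = QT / RR^(1/3), with RR = 60/HR in seconds.
- Heart rate (HR): assumed. The plan gives no distribution. Section 6.3 excludes "Resting bradycardia < 55 beats/min" at entry and sets no upper limit.
- Cycle length: 28 days.

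**Step 1. What the literal rule lets through, and what a QTcF limit would allow**

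Column 2 is 469 / (60/HR)^(1/3). Column 3 is 470 × (60/HR)^(1/3).

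| HR (/min) | QTcF when QT = 469 ms | QT equivalent to QTcF 470 ms |
|---|---|---|
| 55 | 455.6 | 483.8 |
| 60 | 469.0 | 470.0 |
| 65 | 481.7 | 457.6 |
| 70 | 493.7 | 446.5 |
| 75 | 505.2 | 436.3 |
| 80 | 516.2 | 427.0 |

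At 70/min every whole QT value from 447 to 469 ms passes with QTcF of 470 ms or more. At 80/min the range is 428 to 469 ms. Below 60/min the error reverses and the literal rule is stricter than a QTcF limit.

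**Step 2. Crossing points for QT = 469 ms**
- QTcF reaches 470 ms at 60 × (470/469)^3 = 60.4/min.
- QTcF reaches 501 ms at 60 × (501/469)^3 = 73.1/min.

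The second point matters because Section 7.4.1 holds CO-1686 at Grade 3. The plan does not print the grade limits. I assume Grade 3 starts at about 501 ms, the top cut-off in Appendix D Table 3. Above that level the hold rule acts on the reading, so the group left exposed is roughly QTcF 470 to 500 ms.

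**Step 3. Monitoring interval**

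3 cycles × 28 days = 84 days, against 28 days.

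**Step 4. Context only**

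In Appendix D Table 3, post-baseline QTcF of 481 ms or more occurred in 92 + 44 + 7 = 143 of 635 patients, and of 501 ms or more in 59 + 22 + 1 = 82. The difference, 61 of 635 (9.6%), had a highest value of 481 to 500 ms. That table pools 500 to 1000 mg BID at any post-baseline time, so it shows that such values are not rare on this drug. It does not count the patients this rule would affect.

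**The case against.** The strongest reply is that QT here is shorthand for the corrected interval. The plan does use the terms loosely. Section 9.3 restates exclusion criterion 7, written on QT, in terms of QTc. Section 8.1 pairs drugs that prolong QT with monitoring for QTc changes, and the Appendix D text speaks of QT prolongation where its Table 1 says QTc. That makes the corrected reading plausible, perhaps the likelier one. But those places name a phenomenon and none sets a numeric limit. Where the plan does put a millisecond limit on interval length, it uses QTcF, and Section 11.2.5.5 keeps QT apart from it. A site following the sentence as printed has no instruction to correct.

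The second reply is that the reach is narrow, and most of this stands:
- Spacing is optional, starts after Cycle 12 at the earliest, and no new patients enrol.
- Section 3.2.1 places the onset of QTc prolongation in the first 15 days of treatment.
- Tracings go to a central laboratory, and Appendix D keeps the dose rules: "Both the hyperglycemia and QTc management guidelines (Section 7.4) should be followed during this extension phase".
- QTcF of 470 ms is not itself a dose-action limit in the plan.
- A patient restarted at a reduced dose after Grade 3 prolongation qualifies only if QT stayed below 470 ms during that event. On the 501 ms assumption this needs a rate above about 73/min; at 80/min it means QT of 456 to 469 ms.

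These points limit the harm without making the wording right. The hold and discontinuation rules are triggered by ECG readings, and central review sees only tracings that are taken. Fewer ECGs weaken both.

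**Conclusion.** The concern holds as a fault in the wording of an operative safety threshold, and it should be fixed. Read literally, the rule admits patients with QTcF of 470 ms or more at any heart rate above about 60/min, provided QT is close enough to the limit. The gap grows with heart rate: at QT 469 ms the corrected value is 482 ms at 65/min and 494 ms at 70/min. The practical consequence is an ECG interval of about 84 days instead of 28 for some patients at roughly 470 to 500 ms.

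This rests on the standard Fridericia formula, assumed heart rates and an assumed Grade 3 threshold of about 501 ms. The number affected is unknown, because the plan gives no QT or heart-rate data for ongoing patients. If sites already read QT as QTcF, nothing changes in practice.

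**What to change.** In Appendix D, Table 4, footnote h, and in the ECG item under Day 1 of Each Cycle, change the condition to QTcF below 470 ms throughout the study. The cost is two sentences. Some patients would keep ECGs every cycle instead of every third, and a few with heart rates below 60/min might newly qualify for the reduced schedule. If the sponsor meant QTcF all along, the edit only ensures that every site applies the same rule.

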## Day 1 of Each Cycle

Patients receiving CO-1686 are to **refrain** from taking their dose of oral CO-1686 at home on the day of their clinic visit (Day 1 of the cycle) because the dose will be taken during the clinic visit. The following procedures will be completed:

- Physical examination
  - Including a vision check as part of a standard physical exam
- Weight
- Vital signs (blood pressure, pulse, and temperature)
- 12-lead ECG (in triplicate, 10-sec tracings > 2 min apart) prior to dosing, up to and including Cycle 12, at a minimum. For patients who are ongoing at this time and for whom QT has been < 470 ms throughout the study, ECG monitoring may be subsequently taken every 3rd cycle thereafter. ECGs will be performed and interpreted locally for patient care decisions; however, tracings should be submitted to the central lab for independent evaluation. ECGs can be collected at any time pre-dose on the day of the scheduled collection.
- Fasting serum chemistry (including fasting glucose). HbA1c will be measured every other cycle (Day 1 of Cycle 3, 5, 7 etc).
- Hematology (including reticulocyte count)
- Concomitant medication and procedures
- AE monitoring (until 28 days after last dose of protocol specified treatment; then only ongoing SAEs assessed as related to the study drug, and AESIs regardless of causality are followed until resolution or stabilization)
- Collection and review of patient diary and CO-1686 drug return. CO-1686 tablets will be dispensed to the patient; patient diary will be provided to the patient
- Tumor assessments will be performed per institution standard of care or every  $8\pm 1$  weeks after dosing until disease (tumor or clinical) progression. Disease progression to continue to be assessed locally by the Investigator. If a patient discontinues treatment before progression or is continuing treatment post progression (with approval from Sponsor), then the decision to conduct additional scans and the frequency of those scans to monitor disease progression will be the responsibility of the treating physician.
- (Optional) Blood for CYP Evaluation
  - Patient may consent for optional CYP sample collection if not previously collected already, and have the sample collected for NAT2 analysis
  - Sample should only be collected at a single visit

### **End of Treatment Visit**

The following procedures will be performed for all patients 28 days ( $\pm 7$  days) after the last dose of oral CO-1686 or erlotinib:

- Physical examination
   o Including a vision check as part of a standard physical exam
- Weight
- Vital signs (blood pressure, pulse, and temperature)
- Concomitant medications and procedures since last visit
- 12-lead ECG (in triplicate, 10-sec tracings > 2 min apart)
- Fasting serum chemistry (includes fasting glucose).
- Hematology (including reticulocyte count)
- Serum pregnancy test for women of childbearing potential
- AEs/SAEs/AESIs monitoring (until 28 days after last dose of oral CO-1686 or erlotinib; then only ongoing serious adverse events (SAEs) are followed until resolution or stabilization)
- Collection and review of patient diary
- Contraceptive counseling
